24 FEB 2020

[name]

PROTOCOL AMENDMENTS**Amendment 1**

Section	Old text / Content	Amended text / Content	Rationale / Description
1. Protocol Synopsis – Number of Subjects	104	98	Correction
1. Protocol Synopsis – Study Population	66 in Part A	60 in Part A	Correction
1. Protocol Synopsis – Study Population	aged 18 to 55 years (inclusive)	aged 18 to 50 years (inclusive)	Revised the age range to improve screening of healthy volunteers
1. Protocol Synopsis – Study Treatment	within 30 minutes after the end of a...breakfast	approximately 30 minutes after the start of a...breakfast	Correction per FDA guidance on the food effect assessment
4.1.1.3 Nonclinical Safety	Based on these findings, the no observed adverse effect level (NOAEL) was 30 mg/kg/day (Day 28 mean combined sex C _{max} and AUC _{24hr} values of 6.94 µg/mL and 121 µg*h/mL, respectively).	Based on FDA recommendation, a NOAEL of 15 mg/kg/day was considered for calculating the starting dose (mean combined sex C _{max} values was 3.32 µg/mL and AUC _{24hr} 61.2 µg*h/mL).	Revised the rat NOAEL doses and systemic exposure at the NOAEL dose levels per FDA recommendation
4.1.1.3 Nonclinical Safety	Based on the mild severity of findings, the NOAEL was 40 mg/kg/day (Day 28 mean combined sex C _{max} and	Based on FDA recommendation, a NOAEL of 10 mg/kg/day was considered for	Revised the dog NOAEL doses and systemic exposure at the NOAEL dose levels per

	AUC _{24hr} values of 4.18 µg/mL and 40.8 µg*h/mL, respectively).	calculating the starting dose (mean combined sex C _{max} values was 2.61 µg/mL and AUC _{24hr} 21.7 µg*h/mL).	FDA recommendation
4.2.2. Dosing Rationale	...the no observed adverse effect level (NOAEL) was established at 30 mg/kg/day in rats and 40 mg/kg/day (highest dose tested) in dogs...	...the FDA-recommended no observed adverse effect level (NOAEL) doses of 15 mg/kg/day for rats and 10 mg/kg/day for dogs were used for the human starting dose calculations...	Revised the NOAEL doses, systemic exposure, HED and MRSD values per FDA recommendation throughout the text and table presented in this section
7.1. Overview of Study Design	... a total of 72 subjects (66 male...	...a total of 66 subjects (60 male...	Correction
7.1. Overview of Study Design – Table 4	N.A.	Added a footnote of “* Refer to Section 7.1 regarding the subjects returning to the CRU for the food effect assessment.”	Added a footnote for the clarification
8.1. Inclusion Criteria	...18 to 55 years of age	...18 to 50 years of age	Revised the age range to improve screening of healthy volunteers
8.1. Inclusion Criteria	Normal electrocardiogram (ECG) (12-lead), arterial blood pressure (100-140/50-90 mmHg),	Normal electrocardiogram (ECG) (12-lead), arterial blood pressure, and heart rate within the	Revised to clarify the inclusion criteria

	and heart rate (60-100 bpm)	normal range of the study center or considered not clinically significant by the investigator and in agreement with the Sponsor	
9.3. Administration	within 30 minutes after the end of a...breakfast	approximately 30 minutes after the start of a...breakfast	Correction per FDA guidance on the food effect assessment (see above)
9.3. Administration	N.A.	
 • The meal will be taken about 30 minutes prior to the study drug administration. • The meal will be eaten in 30 minutes or less. 	Added the additional instructions on the meal intake for the food effect assessment
9.3. Administration	N.A.	Added the phrase – “with the exception of study-specific events or assessments”	Added for the clarification
9.4.1. Randomization	
The randomization code will be produced by SK Life Science, Inc. designee who will review and approve the randomization list.
 
A copy of the randomization list (in a sealed tamper-evident envelope) will be archived at SK Life Science, Inc.
	
The randomization list will be generated by the clinical research organization (vendor) and will be provided to the site pharmacist. The pharmacist will keep the randomization list
	
Removed the phrase “Study Day 1”;
 
Revised to clarify the randomization process

	
Subjects who have completed screening evaluations and are eligible for participation in the study will be randomized on Study Day 1 for study drug administration.
 
Each randomized subject will be assigned a unique subject number from the randomization list by the investigator or designee, which will be used to identify the individual subject for the duration of the study. The unblinded authorized site personnel will prepare the appropriate study drug/placebo for each subject based on the randomization list.
	
in a secure location.
 
Subjects who have completed screening evaluations and are eligible for the study participation will be randomized for study drug administration.
 
Each randomized subject will be assigned with a unique randomization number.
	
9.4.2. Allocation of Subject Numbers	
Subjects fulfilling the eligibility criteria will be randomized and assigned subject numbers at dosing in the morning of Study Day 1.
 
Subject numbers will be allocated in consecutive order and correspond to a number on the computer-generated randomization list, which determines the treatment (active drug) group. Any replacement subjects will receive the subject number from the subject that they are replacing + 100 (e.g., replacement for subject
	
Subjects fulfilling the eligibility criteria will be randomized to receive their treatment according to the randomization list.
 
Randomized subjects will be assigned with a 4-digit randomization number in the order in which they are enrolled. The first digit of the randomization number will refer to the Cohort
	
Removed the phrase “Study Day 1”;
 
Revised to clarify the randomization process

	
number 01105 would be subject number 01205).
	
number. For example, subjects in Cohort 1 will have the randomization numbers 1xxx; subjects in Cohort 2 will have the randomization numbers 2xxx. In a case where a subject needs to be replaced, the last 2 digits of the randomization number for replacement participants will be identical to those of the original participant's randomization number. The second digit, however, will be replaced with a 2. For example, if the original participant's randomization number is 1101, then the randomization number for the replacement participant will be 1201. Participants who prematurely discontinue from the study may be replaced at the sponsor's discretion.
	
--	---	---	--

9.10.1. Blinding	...assigned to a dosing group linked to their subject number by an unblinded pharmacist at the clinical site.	...assigned to their randomization number linked to the dosing group by an unblinded pharmacist at the clinical site.	Grammar correction; Replaced the “subject number” with “randomization number” for the clarification
9.10.1. Blinding	SK Life Science, Inc. Drug Metabolism and Pharmacokinetics [DMPK] group	SK Life Science, Inc. Toxicology group	Revised to reflect the change of department name
9.10.1. Blinding	randomization code	randomization list	Replaced the “code” with “list” throughout the protocol
9.10.2. Unblinding	...break the code...	...break the blinding...	Replaced the “code” with “blinding” for the clarification
10.3.2. Urine Sampling	N.A.	Added the time window (Table 9) for PK urine sampling	To allow a time window for PK urine sampling
10.3.3.1 Blood Sample Processing	N.A.	... on wet ice...	Added the new text to clarify the sample processing procedure
10.3.3.1 Blood Sample Processing	3000 rpm	2000 xg	Correction for the centrifuge speed
10.6.2. Clinical Laboratory Assessments - Table 10 (Urinalysis)	Occult Blood	Blood	Correction

10.6.3. Physical Examinations and Vital Signs	Vital sign evaluations include blood pressure (systolic and diastolic), temperature, heart rate, respiratory rate, and arterial oxygen saturation (SaO ₂) (using pulse oximetry). These will be assessed following a 5-minute rest in the supine position.	Vital sign evaluations include blood pressure (systolic and diastolic) measurements in supine and standing in the same sequence in each subject, in order to allow orthostatic measurements), temperature, heart rate, respiratory rate, and arterial oxygen saturation (SaO ₂) (using pulse oximetry).	Revised and added the orthostatic measurements with vital sign assessments per FDA recommendation
10.6.4. ECGs	The device will remain connected to the subject during the collection periods.	The device will remain connected to the subject during the collection periods as appropriate.	Added a phrase “as appropriate” to clarify the procedure
10.6.4.1. Safety 12-Lead ECGs	...for 5 minutes...	...for at least 5 minutes...	Correction to keep the time of supine rest consistent throughout the ECG collection
10.6.4.2. Extensive Triplicate ECGs	at least 10 minutes before and 5 minutes during the ECG extraction window to allow for quality ECG data	for at least 5 minutes before the ECG time point in order to allow for quality ECG data	Correction to keep the time of supine rest consistent throughout the ECG collection
10.6.6. Peak Expiratory Flow Rate (PEFR) Measurement	Peak expiratory flow rate (PEFR) will be measured as specified in...	Peak expiratory flow rate (PEFR) will be measured within a 30-minute time window	Added the time window around PEFR

		around the targeted time points as outlined in the Schedule of Assessments in...	
10.6.7.1. Contraception	Subjects who can father a child must agree to use 2 highly effective method of contraception, including at least one barrier method. Subjects must use a condom...	Subjects who can father a child must agree to use 2 highly effective methods of contraception, including at least one barrier method, as follows. Male subjects must use a condom...	Grammar correction by adding the phrase, such as “, as follows” and “Male”
10.6.7.1. Contraception	..., must be in use from...	..., must be used from...	Grammar correction by replacing “in use” to “used”
10.6.7.2. Pregnancy	The investigator must notify the Medical Monitor and SK Life Science, Inc. within 24 hours of the site’s knowledge of the partner’s pregnancy.	The investigator must notify the Medical Monitor, SK Life Science, Inc., and IQVIA by completing the Pregnancy Report form, faxing and emailing the form as per the Table of Contact (Table 13 and Table 14), within 24 hours of the site’s knowledge of the partner’s pregnancy.	Correction to clarify the reporting plans for pregnancy
11. Statistical and Analytical Plans	PK analysis set	PK population	Revised the dataset names - “set” to

			“population” throughout the section per FDA guidance – E9(R1) Statistical Principles for Clinical Trials: Addendum: Estimands and Sensitivity Analysis in Clinical Trials (2017)
11.2. Analysis Populations	Analysis Sets	Analysis Populations	Revised the section header and definition per FDA guidance (see above)
11.2. Analysis Populations	Assignment of subjects to analysis sets will be done prior to clinical database lock. The following analysis sets will be defined: Full Analysis (FA) set, Safety set, and pharmacokinetic (PK) set. • FA set: All randomized subjects, whether or not they received study drug. Subjects will be analyzed according to the study drug to which they were randomized. All non-safety summaries (e.g., demographics) will be prepared using the FA set, as appropriate.	N.A. (Removed the old text as shown)	Deleted the old text to revise the dataset names (see above); Replaced the phrase “FA set” with “Safety Population” throughout the section

11.2. Analysis Populations	Safety set: All subjects who received at least 1 dose of study drug. Subjects will be analyzed according to the study drug actually received. All summaries of safety will be referenced using the Safety set.	Safety Population: All subjects who were randomized and received at least 1 dose of study drug.	Revised the definition for the clarification
11.2. Analysis Populations	PK set: All subjects who satisfied the PK evaluation criteria and dosed with the study drug without any major protocol violations and with sufficient PK profiles	PK population: All subjects who received at least 1 dose of study drug and have sufficient PK data without any major protocol deviations.	Revised the definition for the clarification
11.4.2.2. Demographics and Baseline Characteristics	Demographic, background, and baseline characteristics will be summarized for the FA set and will include (but are not limited to) subject disposition, demographics, baseline characteristics, medical history, and prior medications. Continuous variables will be summarized by descriptive summary statistics and categorical variables by frequency tables.	Demographic, parameters and baseline characteristics will be summarized for the Safety Population. Continuous variables will be summarized by descriptive summary statistics and categorical variables by the number and percentage of participants.	To clarify, the following changes were made: 
1. Replaced the word “background” with “parameters”;2. Corrected the redundant phrases;3. Replaced the “frequency tables” with “number and percentage of participants”;4. Deleted the redundant statement as shown

11.4.2.3. Medical History	N.A.	Medical history encompassing abnormalities and surgeries reported before the Screening visit will be coded using the Medical Dictionary for Regulatory Activities (MedDRA), version 19.0 or newer.	Added a new section 11.4.2.3. in order to improve the statistical analysis plan
11.4.2.4. Prior and Concomitant Medications	
...regardless of whether medication end date is missing or not.
 
...regardless of whether medication start date is missing or not. Note that medication that started prior to initial dosing of the study drug and continued after initial dosing will be summarized as prior medication and separately as concomitant medication.
	
...regardless of the medication end date. ...regardless of the medication start date. The prior and concomitant medications will be summarized separately.
	Grammar correction and clarification
11.4.4.4. Vital Signs	systolic and diastolic blood pressure (mmHg)	systolic and diastolic blood pressure (mmHg) measurements (in supine and standing in the same sequence in each subject, in order to allow orthostatic measurements)	Added the orthostatic measurements with vital sign assessments per FDA recommendation

12.2.2. Subject Information and Informed Consent	N.A.	A subject identification number (subject ID) will be assigned to each subject at the time that informed consent is obtained; this subject ID will be used throughout the study.	Added the new text to clarify as shown
--	------	---	--

Amendment 2

Section	Old text / Content	Amended text / Content	Rationale / Description
9.4.2. Allocation of Subject Numbers	Randomized subjects will be assigned with a 4-digit randomization number in the order in which they are enrolled. The first digit of the randomization number will refer to the Cohort number. For example, subjects in Cohort 1 will have the randomization numbers 1xxx; subjects in Cohort 2 will have the randomization numbers 2xxx. In a case where a subject needs to be replaced, the last 2 digits of the randomization number for replacement participants will be identical to those of the original participant's randomization number. The second digit, however, will be replaced with a 2. For example, if	Randomized subjects will be assigned with a 6-digit randomization number in the order in which they are enrolled. The first digit of the randomization number will refer to the part A or B (1 or 2). The second and third digits will refer to the Cohort number. For example, subjects in Cohort 1 of part A will have the randomization numbers 101xxx; subjects in Cohort 2 of part A will have the randomization numbers 102xxx.	Changed 4-digit randomization number to 6-digit in order to accommodate part A and part B. Add one more digit to accommodate more cohorts.

	
the original participant's randomization number is 1101, then the randomization number for the replacement participant will be 1201. Participants who prematurely discontinue from the study may be replaced at the sponsor's discretion.
	
In a case where a subject needs to be replaced, the last 2 digits of the randomization number for replacement participants will be identical to those of the original participant's randomization number. The fourth digit, however, will be replaced with a 2. For example, if the original participant's randomization number is 110101, then the randomization number for the replacement participant will be 110201. Participants who prematurely discontinue from the study may be replaced at the sponsor's discretion.
	
--	--	--	--

Amendment 3

Section	Old text / Content	Amended text / Content	Rationale / Description
2.0. Schedule of Assessments: Table 1	N.A.	Added Pregnancy Test (Serum) at screening and admission (Day -1). Adjusted footnote letters.	Revised schedule of assessments to add pregnancy test to gender effect cohort. Added a footnote for clarification.
8.1. Inclusion Criteria	1. Male subjects of 18 to 50 years of age (inclusive).	1. Male subjects of 18 to 50 years of age (inclusive) except for the gender effect cohort.	Revised to clarify the gender effect cohort will enroll healthy female subjects of non-childbearing potential.
8.1. Inclusion Criteria	8. For Part A (gender effect cohort): Female of non-childbearing potential (18 to 50 years of age (inclusive)), who have undergone a sterilization procedure at	8. For Part A (gender effect cohort): Female of non-childbearing potential (18 to 50 years of age (inclusive)), who have undergone a sterilization procedure at least 6 months prior to dosing with official documentation (e.g., hysteroscopic	Added pregnancy test for screening and admission (Day -1).

	least 6 months prior to dosing with official documentation (e.g., hysteroscopic sterilization, bilateral tubal ligation or bilateral salpingectomy, hysterectomy, or bilateral oophorectomy), or be postmenopausal with amenorrhea for at least 1 year prior to dosing and follicle-stimulating hormone (FSH) serum levels consistent with postmenopausal status as per Principal Investigator's judgment	sterilization, bilateral tubal ligation or bilateral salpingectomy, hysterectomy, or bilateral oophorectomy), or be postmenopausal with amenorrhea for at least 1 year prior to dosing, a follicle-stimulating hormone (FSH) serum levels consistent with postmenopausal status and serum pregnancy test at screening and upon admission with a negative result as per Principal Investigator's judgment	
9.4.2 Allocation of Randomization Numbers	Allocation of Subject Numbers	Allocation of Randomization Numbers	Revised to correct wording

1. PROTOCOL SYNOPSIS

Title A Phase 1, Randomized, Double-Blinded, Single-Dose Escalation Study Followed by a Multiple-Dose Escalation Study of SKL24741 in Healthy Subjects

Clinical Phase Phase 1

Objectives **Part A (single dose administration)**

Primary:

- To evaluate the safety and tolerability of single oral ascending doses of SKL24741 capsule(s) administered to healthy male subjects

Secondary:

- To evaluate the pharmacokinetics (PK) of SKL24741 (R-enantiomer), SKL24742 (S-enantiomer) (if appropriate), and its possible metabolites (if deemed necessary) following administration of single oral ascending doses of SKL24741 capsule(s) administered to healthy male subjects
- To assess the food effect on the PK of SKL24741 and SKL24742 (if appropriate) following administration of a single oral dose of SKL24741 capsule(s) administered to healthy male subjects
- To assess the gender effect on the PK of SKL24741 and SKL24742 (if appropriate) following administration of a single oral dose of SKL24741 capsule(s) administered to healthy female subjects

Part B (multiple dose administration)

Primary:

- To evaluate safety and tolerability of multiple oral ascending doses of SKL24741 capsule(s) administered for 14 days to healthy male subjects

Secondary:

- To evaluate the PK of SKL24741, SKL24742 (if appropriate), and its possible metabolites (if deemed necessary) following administration of multiple oral ascending doses of SKL24741 capsule(s) administered to healthy male subjects

Endpoints Primary:

- Safety and tolerability will be based on assessment of adverse events, clinically significant laboratory assessments, electrocardiograms (ECGs), peak expiratory flow rate (PEFR), vital signs (blood pressure, heart rate, body temperature, respiratory rate,

arterial oxygen saturation (SaO_2) (using pulse oximetry)), physical examinations, and Columbia-Suicide Severity Rating Scale (C-SSRS) (Part B only).

Secondary:

- PK parameters will be calculated for SKL24741 and SKL24742 (if appropriate) from plasma and urine PK data.

Number of Subjects 98

Study Population Healthy male subjects (60 in Part A and 32 in Part B), aged 18 to 50 years (inclusive)
Healthy female subjects (non-childbearing potential) (6 in Part A), aged 18 to 50 years (inclusive) for gender effect cohort of Part A

Investigational Drug Active substance: SKL24741
Activity: An inhibitor of voltage-gated sodium channels and a possible activator of Big Potassium channels
Dosage Form: Capsule
Route of Administration: Oral

Study Treatment	Part	Doses
	A	A single oral dose of 10, 25, 50, 100, 200, 300, 400, 600, 800, and 1000 mg of SKL24741 or placebo will be administered to subjects in the morning of the first day, following an overnight (10-hour) fast (all doses) or approximately 30 minutes after the start of a high-calorie, high-fat breakfast (Food effect cohort).
	B	Multiple oral administrations of 4 dose levels of SKL24741 or placebo administered to male subjects each day for 14 days. Dose, dosing regimen, and food status (fasting vs. fed) used in Part B will be determined based on the outcome of Part A.

Schedule of Study Visits Subjects in **Part A** will remain in the clinic for a 4-night stay (discharged on Study Day 4). Subjects in **Part B** will remain in the clinic for a 17-night stay (discharged on Study Day 17). There will be one Follow-up visit 14 to 16 days after the last dosing occasion for all subjects.

Pharmacokinetic Evaluations Plasma Samples for Bioanalytical (BA) Analysis
Part A

- Pre-dose, and 0.25, 0.5, 1, 2, 3, 4, 6, 8, 10, 12, 16, 18, 24, 36, 48, 60, and 72 hours post-dose following the single dose administration

Part B

- **Study Days 1 and 7:** Pre-dose, and 0.25, 0.5, 1, 2, 3, 4, 6, 8, 10, 12, 16, and 24 hours post-dose. The 24-hour post-dose blood PK samples for Days 1 and 7 should be taken before dosing on Days 2 and 8, respectively
- **Study Days 3 to 6 and 9 to 13:** Pre-dose only
- **Study Day 14:** Pre-dose, and 0.25, 0.5, 1, 2, 3, 4, 6, 8, 10, 12, 16, 18, 24, 36, 48, 60, and 72 hours post-dose

Urine Samples for Bioanalytical (BA) Analysis

Part A

- Pre-dose, and 0 to 4, 4 to 8, 8 to 12, 12 to 24, 24 to 48, and 48 to 72 hours post-dose following the single dose administration
- No urine collection for PK analysis in the food and gender effect cohorts

Part B

- No urine collection for PK analysis in Part B

Safety Evaluations Adverse events, clinical laboratory assessments, electrocardiograms (ECGs), peak expiratory flow rate (PEFR), vital signs (blood pressure, heart rate, body temperature, respiratory rate, arterial oxygen saturation (SaO₂) (using pulse oximetry)), physical examinations, and Columbia-Suicide Severity Rating Scale (C-SSRS) (Part B only)

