Assessment	Screening	Admission	Confinement																Follow-up (14 – 16 days after final dosing day)	
	Study Day																			
Assessment	-28 to -2	-1	1	2	3	4	5	6	7	8	9	10	11	12	13	14	15	16	17	28 to 30
Urinalysis ^j	X	X			X					X							X		X	X
Alpha-1-acid Glycoprotein	X																			
Total, LDL, and HDL Cholesterol	X																X		X	
C-SSRS	X																X			X
PK Sampling – Plasma ^k			X ^k	X	X	X	X	X	X ^k	X	X	X	X	X	X	X ^k	X ^k	X ^k	X	
PGX Sampling – Whole blood ^l		X																		
Study Drug Dosing ^m			X	X	X	X	X	X	X	X	X	X	X	X	X					
Adverse Event Assessment and Reporting	Ongoing from the time of signing the Informed Consent Form (Non-treatment and Treatment emergent adverse events)																			

^a Subjects will be admitted to the clinic the day prior to study drug administration.

^b Subjects will be discharged on Study Day 17, after the 72-hour PK sample from the final dose has been collected and the final assessment has been completed.

^c At screening, a separate informed consent form (ICF) will be used to obtain the subject's consent for the utilization of their DNA for pharmacogenomic (PGX) testing.

^d For drugs of abuse/alcohol screen, refer to Section 10.6.2. At the time of signing the ICF, a negative result from the breath alcohol test is required.

^e Complete physical examination should be performed at screening only. Abbreviated physical examination should be performed at all other marked study days. See Section 10.6.3.

^f Height and weight will be collected, and BMI calculated at screening. Only weight will be collected at FU.

^g Highlighted time points for vital signs (Section 10.6.3) as follows: pre-dose (baseline), 1, 2, 3, 4, 6, 8, and 12 hours post-dose on Day 1; pre-dose, and at 2, 6, and 8 hours post-dose on Days 2 through 14. Vital signs should be assessed at all other marked study days.

^h Peak expiratory flow rate will be assessed at admission (Day -1), pre-dose (baseline), 2 and 24 hours post-dose after the first dose (Day 1 dosing) and the last dose (Day 14 dosing), and FU.

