Part B is a multiple-dose escalation study in 32 healthy male subjects. Doses, dosing regimen, and food status (fasting vs. fed) used in Part B will be determined based on the outcome of Part A. Dosing will extend over a 14-day period at each dose level. Four dose levels will be assessed, and subjects will be randomized into one of the four dose levels. Each dosing cohort will have 8 new subjects (6 subjects randomized to SKL24741 and 2 to placebo) dosed each day for 14 days ([Table 4](#)). Daily dose level in Part B will not exceed the maximum dose level used in Part A.

At each dose level, a sentinel dosing strategy will be used as described in Section [7.2](#).

Table 4: Study Design

Part A: Single Ascending Doses (SAD)			
Total Number of Subjects	Randomized Stratification (Active/Placebo)	Number of Subjects per Cohort	Food Status (Fasting/Fed)
60 Male Subjects	10 mg SKL24741/Placebo	4 SKL24741/ 2 Placebo	Fasting

	25 mg SKL24741/Placebo	4 SKL24741/ 2 Placebo	Fasting
	50 mg SKL24741/Placebo	4 SKL24741/ 2 Placebo	Fasting
	100 mg SKL24741/Placebo	4 SKL24741/ 2 Placebo	Fasting
	200 mg SKL24741/Placebo	4 SKL24741/ 2 Placebo	Fasting
	300 mg SKL24741/Placebo	4 SKL24741/ 2 Placebo	Fasting
	400 mg SKL24741/Placebo	4 SKL24741/ 2 Placebo	Fasting
	600 mg SKL24741/Placebo	4 SKL24741/ 2 Placebo	Fasting
	800 mg SKL24741/Placebo	4 SKL24741/ 2 Placebo	Fasting
	1000 mg SKL24741/Placebo	4 SKL24741/ 2 Placebo	Fasting

Part A: Food Effect Assessment

Total Number of Subjects	Dose	Number of Subjects per Cohort	Food Status (Fasting/Fed)
6 Male Subjects*	Based on the outcome of Part A	6 SKL24741	Fed

Part A: Gender Effect Assessment

Total Number of Subjects	Dose	Number of Subjects per Cohort	Food Status (Fasting/Fed)
6 Female Subjects (non-childbearing potential)	Based on the outcome of Part A	6 SKL24741	Fasting

Note:

- All doses are in a capsule formulation.
- Subjects will remain in the clinic for a 4-night stay (discharged on Study Day 4).
- A sentinel dosing strategy (Section 7.2) will be used for all cohorts, except for food and gender effect cohorts, in Part A.

* Refer to Section 7.1 regarding the subjects returning to the CRU for the food effect assessment.

Part B: Multiple Ascending Doses (MAD)

Total Number of Subjects	Randomized Stratification (Active/Placebo)	Number of Subjects per Cohort	Food Status (Fasting/Fed)
32 Male Subjects	SKL24741 Dose 1/Placebo	6 SKL24741/2 Placebo	Based on the outcome of Part A

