10.6.5. Columbia-Suicide Severity Rating Scale

The Columbia-Suicide Severity Rating Scale (C-SSRS) is a brief questionnaire that provides for the identification, quantification, and standardized assessment of the occurrences and severity of suicidal ideation and behavior. The C-SSRS will be assessed only after multiple dose administration (Part B). The “Baseline (Lifetime/Recent)” version of the C-SSRS will be assessed at screening ([Appendix C](#)). The C-SSRS “Since Last Visit” version will be assessed on other study days ([Appendix D](#)).

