11.4.4.7. Columbia-Suicide Severity Rating Scale (Part B only)

Columbia-Suicide Severity Rating Scale (C-SSRS) results will be summarized by treatment group and by part of the study at each study day of assessment. The raw values, changes from baseline, and clinical abnormalities will be summarized as appropriate. Baseline will be defined in the study SAP. Clinically significant abnormal findings will be reported as adverse events.

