12.1.2. Routine Reporting

For the purposes of this study, the period of observation of adverse events for each subject extends from the signing of the informed consent form until their last visit including the follow-up visit or early termination, whichever is longer.

All events reported by the subject, observed by the clinical staff (events, such as abnormal, clinically significant findings from physical examinations, ECG tracings, laboratory assessments, and vital sign measurements), or elicited by general questioning will be recorded in the Institution's source document and reported as an adverse event and captured in the adverse events CRF. If necessary, every effort will be made to obtain an adequate

follow-up of the subjects. Should any subject choose to withdraw early from the study, they will be advised of the safety precautions to be taken.

Early Termination and End of Study (EOS) visit assessments should be performed, including the following: medical history, vital signs, physical exam, safety and clinical laboratory tests, ECG, peak expiratory flow rate (PEFR), Columbia-Suicide Severity Rating Scale (C-SSRS), and adverse event/concomitant monitoring.

Subjects will be questioned on their health status at the beginning of each visit and before their departure from the clinical site. Open-ended questions will be asked.

Classification will be performed by System Organ Class (SOC) and Preferred Term (PT) using the latest version of Medical Dictionary for Regulatory Activities (MedDRA) at the start of the study.

In general, AEs occurring secondary to other events (e.g., clinical sequelae or a cascade of events) should be identified by their primary cause. For example, if severe vomiting is known to result in dehydration, it is sufficient to record only vomiting as SAE or AE in the CRF. However, medically significant AEs occurring secondary to an initiating event that are separated in time should be recorded as independent events on the CRF.

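### Part B has no C-SSRS form between screening and the first dose, and the look-back of the Day 15 form is undefined, so pre-dose ideation can be counted after dosing or missed

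*Protocol*

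**What the plan says.** The synopsis (Endpoints) includes "physical examinations, and Columbia-Suicide Severity Rating Scale (C-SSRS) (Part B only" among the primary safety and tolerability assessments, and Section 6.1 repeats this.

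Table 2 marks the C-SSRS at three points: screening (Day -28 to -2), Day 15 and Follow-up (Day 28 to 30). Admission on Day -1 and Days 1 to 14 are blank.

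Section 10.6.5 says "The C-SSRS will be assessed only after multiple dose administration (Part B". It states that the Baseline (Lifetime/Recent) "version of the C-SSRS will be assessed at screening", and that the Since Last Visit "version will be assessed on other study days". It does not define the last visit.

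Section 7.1 says of Part B: "Dosing will extend over a 14-day period at each dose level".

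Section 11.4.4.7 says that C-SSRS "results will be summarized by treatment group and by part of the study at each study day of assessment". It leaves the definition of baseline to the SAP and has clinically significant findings reported as adverse events. Section 11.4.4.1 calls an event treatment-emergent when it is reported, or worsens, once study medication has started.

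Section 12.1.2 says "Early Termination and End of Study (EOS) visit assessments should be performed" and includes the C-SSRS among them, so subjects who leave early get an additional form.

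**The concern.** A Since Last Visit form covers an interval. To describe the period on drug, that interval should start at about the first dose. Here the only earlier form may be up to 28 days before dosing, and nothing is recorded in between.

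The other scheduled primary safety components do not share the gap. In Table 2, laboratory tests, safety ECG, vital signs, peak flow and physical examination all have a Day -1 reading, and vital signs, peak flow and triplicate ECG also have a pre-dose one.

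The groups are small: four cohorts of 6 active and 2 placebo subjects. One positive form is 1/6 = 16.7% of a dose group, or 1/8 = 12.5% of pooled placebo. Whether a single positive answer belongs before or after the first dose can therefore settle how the scale is read.

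**Working it through.** The protocol gives no figure to reproduce; the check is day arithmetic on Table 2.

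**Inputs.** Screening is Day -28 to -2, admission Day -1, first dose Day 1, and there is no Day 0 (Table 2 header). Dosing lasts 14 days (Section 7.1). Forms are at screening, Day 15 and Follow-up (Table 2, C-SSRS row).

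**Formulas.** For screening on Day -s, pre-dose days = s. From Day 1 to a form on Day d there are d - 1 days. Look-back = s + (d - 1).

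**Reading 1: the last visit is the previous C-SSRS (screening).**
- Screened Day -28: 28 + 14 = 42 days; pre-dose share 28/42 = 66.7%.
- Screened Day -2: 2 + 14 = 16 days; pre-dose share 2/16 = 12.5%.

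**Reading 2: the last visit is admission (Day -1).**
- Day 15 look-back: 1 + 14 = 15 days; pre-dose share 1/15 = 6.7%.
- Interval covered by no form, screening to admission: 28 - 1 = 27 days at most, 2 - 1 = 1 day at least.

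The first reading mixes pre-dose and dosing time. The second nearly removes the mixing but leaves a gap, with a baseline up to four weeks old.

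**Is the Day 15 mark secure?** In the text copy of Table 2 the C-SSRS row has the right number of cells (20 day columns), and the plasma PK row beside it agrees with its footnote. The dosing row, however, shows 13 marks for 14 doses, so a slip of one column cannot be excluded. Were the mark on Day 14, Reading 1 would give 28 + 13 = 41 days (28/41 = 68.3%) down to 2 + 13 = 15 days (2/15 = 13.3%). The pre-dose part is still 2 to 28 days.

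**Follow-up form.** It falls 28 - 15 = 13 to 30 - 15 = 15 days after Day 15. If it looks back to Day 15, its interval lies wholly after the first dose, so the problem is confined to the first form after screening, or to an early-termination form that takes its place.

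**Can the analysis recover the timing?** In Appendix E the ideation items have a yes/no box and a free-text description but no onset date; only actual attempts have a date field. Section 11.4.4.1 turns on when an event is reported or worsens. Ideation from before dosing but first disclosed on Day 15 is reported after study medication began, so read literally it qualifies as treatment-emergent. Section 11.4.4.7 would also place it in the Day 15 row of its treatment group.

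**The case against.** The strongest reply is that the 2 to 28 pre-dose days depend on an undefined term. Admission is a separate attendance with its own checks, and if it counts as the last visit only about one pre-dose day is included. That stands: the long look-back is one of two readings. The other reading does not rescue the schedule, because it leaves the time before admission unrecorded.

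Second, clinically significant findings become adverse events, which are collected from consent and classed as pre-treatment or treatment-emergent, and the free text may give the timing. This is a real route, but nothing requires the text to give a date, and the classification uses the time of reporting.

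Third, Section 11.4.4.7 fixes no on-treatment counting rule and leaves baseline to the SAP. Deferring that definition is no fault. The fault is in what is collected: an SAP can define a reference point but cannot date an undated answer.

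Fourth, placebo subjects have the same look-back, so neither arm is systematically favoured. This is correct. The effect is misclassification in very small groups, not a directional bias.

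A reader might also infer that the scale cannot inform decisions about the rest of a cohort. The documents do not support that. At the first dose level Table 5 gives a 14-day sentinel observation period, which ends at about Day 15. Adverse events are collected throughout, Section 10.6 provides ongoing medical review, and leavers have a C-SSRS at early termination. What holds is narrower: at higher dose levels the 7-day sentinel review, at about Day 8, has no scheduled C-SSRS after screening.

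**Conclusion.** The point holds as a gap in the schedule joined to an undefined look-back. A named primary safety component of Part B has no reading between screening and the first dose. Depending on what the last visit means, either 12.5% to 67% of the Day 15 look-back is pre-dose, or 1 to 27 days before admission are covered by no form. This rests on Table 2 being read as screening, Day 15 and Follow-up; a shift to Day 14 leaves the conclusion unchanged.

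Two stronger statements are not supported. One might assume a daily background rate of ideation and compute the chance of a misplaced positive, but the protocol gives no such rate and the result would only reflect the assumption. One might also call the absence of a form on Days 1 to 14 an error in itself. Section 10.6.5 appears to intend assessment after dosing, the Day 15 form covers the dosing period in retrospect, and a form during dosing is largely a matter of preference.

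**What to change.** - **Table 2:** add one Since Last Visit form at Day 1 pre-dose, or at Day -1 treated as the pre-dose baseline.
- **Section 10.6.5:** state that each form looks back to the previous C-SSRS, and reword the sentence on assessment only after multiple dosing so that it allows the pre-dose form.
- **Section 11.4.4.7:** use the pre-dose form as the reference and count as post-dose only answers from later forms. The rule should not require a look-back that starts at or after the first dose: with a Day -1 form, that would exclude the next form and the dosing days it covers.

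Section 11.4.4.1 can stay as it is, because ideation disclosed on the pre-dose form is then reported before study medication starts. If Day -1 is chosen, about one pre-dose day remains in the next form.

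The cost is 1 x 32 = 32 short questionnaires in subjects already confined, with no added visit. A further form at about Day 8, which could serve the 7-day sentinel review, is optional and would add up to another 32.
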